Inguinal hernia surgery is one of the most common elective operations around the world. It was significantly down-prioritised during the pandemic, with fewer planned procedures and a likely increase in a global backlog³. According to the most updated data, there are 74,822 patients waiting for inguinal hernia repair in the United Kingdom's National Health Service (NHS),⁶ although the recommended expected waiting time should not exceed 18 weeks⁷. It is likely that other countries face the same problem, although such granular data does not exist.⁸ Additionally, while waiting for an elective repair, complications of inguinal hernia might arise and an emergency surgery might be needed. Identifying the scale of the global backlog at a global level will inform policy makers on the best strategies to optimise this elective surgical pathway.

Different surgical techniques exist, with different mesh and non-mesh techniques being described. The most up-to-date international guidelines recommend Lichenstein as the gold-standard for open repair of inguinal hernias, but a more tailored approach is recommended. The patient, the hernia type, and the surgeon's expertise will influence the choice of surgical technique which leads to a wide variation worldwide. Additionally, in areas where there is a deficit of surgeons, task sharing and task shifting might be implemented 10,11. Identification of this practice across the world and the outcomes associated with it will inform future research in this area.

Finally, as inguinal hernia repair is a very common procedure, it can reflect the global uptake of environmentally sustainable measures in elective surgery⁵. Achieving a net zero health system is only possible if reducing the carbon output from operating theatres is included. Different

countries might have different protocols and measures adopted to be environmentally sustainable that could be used in different settings. Understanding the baseline point of these practices is extremely important to inform future studies in this area.

Audit Standards

Pre-operative standards

NHS UK: Inguinal Hernia Repair⁷

• Waiting times: The maximum recommended waiting time for inguinal hernia surgery in the NHS is 18 weeks after referral from the GP

Intraoperative standards

International guidelines for groin hernia management9

Mesh repair: Mesh repair is recommended as first choice, either by an open procedure or a laparoendoscopic repair technique. Lichtenstein and laparo-endoscopic repair are best evaluated.

International guidelines for groin hernia management9

Non-mesh repair: If a non-mesh repair is selected, the Shouldice technique is the gold standard for open inguinal hernia repair without mesh

International guidelines for groin hernia management⁹:

Laparoscopic repair: Where resources and expertise are available, laparo-endoscopic repair have faster recovery times. For the repair of primary bilateral inguinal hernia, laparo-endoscopic repair is recommended, where there is specific expertise and sufficient resources. When laparoscopic surgery is undertaken for inguinal hernia, as TAPP and TEP have comparable outcomes, the choice of technique should be based on surgeon's experience.

Methods

1. Summary

A prospective, multicentre, cohort study will be delivered by NIHR Unit on Global Surgery globally. Mini-teams of up to five collaborators per data collection period will prospectively collect data over a continuous 28-day period at each participating centre. This will be on consecutive patients undergoing elective and/or emergency primary inguinal hernia surgery, with follow-up to 30 postoperative days.

2. Study Aims:

• Primary Aim: To identify compliance to audit standards described

Secondary Aims

- o To understand the impact of waiting times in inguinal hernia patients
- To explore technical variation of inguinal hernia surgery
- o To explore surgical outcomes of inguinal hernia repair done by non-surgeons
- o To identify environmentally sustainable measure adopted by operating teams

3. Project Timeline:

- The suggested overall data collection periods will be Monday 30th January 2023 to 21st May 2023, with the possibility of extending for 1 more month, considering that the ethical review process might take different times in each country. Each mini-team will collect data over a 28-day, (4 weeks) consecutive period with subsequent 30-day follow-up:
 - o Period 1: 00:00 30th Jan 2023 23:59 26th Feb 2023 (+ 30 Day Follow-up)
 - o Period 2: 00:00 27th Feb 2023 23:59 26th Mar 2023 (+ 30 Day Follow-up)
 - o Period 3: 00:00 27th Mar 2023 23:59 23th Apr 2023 (+ 30 Day Follow-up)
 - o Period 4: 00:00 24th April 2023 23:59 21st May 2023 (+ 30 Day Follow-up)
- Patients should be included if their operation started (defined as 'knife-to-skin' time) within the time period during the data collection periods as specified above.

4. Centre Eligibility:

- HIPPO is open to any hospital globally that performs inquinal hernia surgery
- All participating centres are required to register the HIPPO study according to local regulations. In the UK, HIPPO should be registered as an audit.

- Outside of the UK, individual study investigators are responsible for ensuring the correct audit, ethical or departmental approval has been achieved prior to commencing data collection (this can be registered as an audit or service evaluation, if appropriate).
- Centres will not be allowed to upload patients' data onto REDCap until they have successful registration of the study.

5. Patient Eligibility:

Summary: Consecutive patients during the selected study period undergoing elective or emergency primary inquinal hernia repair through any operative approach.

Inclusion criteria:

- Age: Paediatric and adult patients
- Procedure: Primary inguinal hernia repair, where this is the main procedure. For
 patients with bilateral inguinal hernias, data should be entered only for the larger of the
 two.
- Approach: Open groin incision, laparoscopic, laparoscopic assisted, laparoscopic converted, robotic, robotic converted procedures are all eligible. Patients with open incisions other than groin incision (e.g. laparotomy) are excluded.
- **Urgency**: Patients undergoing planned (elective) surgery or emergency surgery

Exclusion criteria:

Procedures:

- Recurrent inguinal hernias
- Surgeries where inguinal hernia repair is not the main procedure, but performed as an additional procedure (eg patient operated for colon cancer and undergoing inguinal hernia repair during the same operation).
- o If patients are undergoing repair of two different types of hernia they can be included if the inguinal hernia repair is the main operation. (e.g. patient undergoing both inguinal and umbilical hernia repair). However, if the inguinal hernia repair is a secondary procedure to a larger non-inguinal hernia repair, patients should be excluded (e.g patient undergoing both large incisional hernia repair and inguinal hernia repair).
- Laparoscopic converted to open midline procedures.
- Patients undergoing surgery with intent of repair of inguinal hernia, where no hernia inguinal hernia was identified (e.g. intra-operative findings of adenopathy, femoral hernia, obturator hernia)

• Return to theatre:

- Each individual patient should only be included in the study once. Patients returning to theatre due to complications following earlier surgery can only be included if their index procedure has not already been included in the HIPPO audit.
- Patients with bilateral hernias undergoing repair with two separate procedures in two different times, should only be included for the first procedure.

6. Patient identification:

You should collect data on consecutive patients operated at your centre during the data collection period. This means that all eligible patients should be included to avoid selection bias.

Strategies to identify consecutive eligible patients could include:

- Daily review of elective and emergency theatre lists.
- Daily review of handover sheets and ward lists.
- Daily review of theatre logbooks (both elective and emergency).

7. Other variables:

Data will be collected on audit standards and confounding factors for risk-adjusted analyses. These include age, sex, body mass index, American Society of Anaesthesiologists (ASA) grade, relevant comorbidities, and smoking status. Variables including inguinal hernia features assessed pre-operatively, anaesthesia type, operative approach and technique will also be collected. Without appropriately adjusting for risk factors, it is likely that any findings would be biased and unable to be appropriately analysed on a national scale. A full list of required data fields is available in the Data Summary Document, and on the REDCap database.

8. Outcome Measures and Follow-up:

Primary outcome measure:

Compliance to audit standards described

Secondary outcome measures: (see Appendix A:)

- 30-day follow-up
- 30-day surgical site infection rates
- 30-day reoperation rates
- 30-day readmission
- 30-day Clavien-Dindo complications

Follow-up should be performed in line with current routine practice within each hospital settings. No additional telephone, in-person or questionnaire-based follow-up is required. Source data may be acquired from hospital in-patient notes, clinical electronic systems, or outpatient letters.

9. Data collection processes and governance:

This project will involve the formation of mini-teams of 1-5 collaborators. Mini-teams will include a specialist consultant at each site. These teams will prospectively collect data in up to 4 continuous 28-day periods on all eligible patients undergoing inguinal hernia surgery. To ensure data is collected on all consecutive eligible patients these teams will review elective theatre lists, handover sheets/emergency admission and ward lists, and theatre logbooks (both elective and emergency) on a daily basis.

Following the identification of an eligible patient undergoing inguinal hernia surgery within a study data collection time period, the patient will be added to a Patient Identification Log. This log will be a way to link the patient Medical Record Number (MRN) with the study Research Electronic Data Capture (REDCap) Database to facilitate data entry and missing data requests. This is a site-specific document, that will include the patient MRN and a unique REDCap ID (only). The hardcopy Patient Identification Log must be stored in a secure location at each site. The patient identification log will not be uploaded or transferred electronically or provided to any member of the research team outside of each hospital site.

All study data (as outlined in the Data Summary Document) will be recorded directly into the REDCap study database and will not be recorded in paper format. All data recorded in the

REDCap database will be de-identified, with all direct and indirect identifiers irrevocably removed by each site, with no way to re-identify the data by the NIHR Unit on Global Surgery.

The Principal Investigator at each site must ensure that the study team observe local data governance and national privacy regulations. A start-up meeting will be conducted in Australia prior to the collection of study data to overview the protocol, local procedures, and Australian data privacy regulations.

Since the HIPPO study is a prospective study, the study team will be required to continue to review the medical record of each participant for a period of 30 days following the date of surgery. Individual sites will create their own system to manage this process that is best suited to their site and team requirements. The process will be facilitated by The Patient Identification Log. This log will be confidentially destroyed by each participating site immediately following the completion of the data collection phase of the study (15th July, 2023).

De-identified study data will be collected and stored online through a secure server running the Research Electronic Data Capture (REDCap) web application, 13,14 allowing safe anonymised data storage by collaborators internationally. The service is managed by the Global Surgery REDCap system hosted at the University of Birmingham, United Kingdom. The security of the study database system is governed by the policies of the University of Birmingham. These include appropriate best practices such as network firewalls, system and security monitoring and two factor authentication. REDCap access privileges will be managed and maintained by the NIHR Unit on Global Surgery to ensure that users can only access data relevant to their site. That is, each site user will only have access to their site's data.

Data management and data security within the BiSTC REDCap will abide by the requirements of the General Data Protection Regulations (GDPR) and any subsequent amendments. Collaborators will be given secure REDCap project server login details, allowing secure data storage on the REDCap system.

All study data will be collected through patient information systems including accessing both written and electronic hospital records. These records will include patient charts, medication charts, investigation results, theatre notes, discharge summaries, relevant letters from outpatient clinics and surgeons' rooms. Refer to the Data Summary Document for details of all deidentified datafields to be entered in the REDCap Database.

No patient data will be uploaded or stored on the REDCap database without prior local permissions. All data should be handled in accordance with local data governance policies, and all study documents should be destroyed as confidential waste within the site at the completion of the study, or according to the local governance requirements. Data collected during the HIPPO study can be used for future analyses at the Study Management Group's discretion.

10. Data Analysis & Sample Size:

Based on previous GlobalSurg-CovidSurg studies HIPPO is anticipated to include around >1000 centres globally. With recent figures provided by previous GlobalSurg-CovidSurg Week study¹⁵, a sample of approximately 5,000 patients is anticipated. No surgeon-, hospital- or country-specific comparisons will be performed. Further secondary analyses may be performed at the Study Management Group discretion.

11. Local Project Registration:

This project may be registered as clinical audit or service evaluation. Alternatively, it may be necessary to obtain formal ethical approval. In Australia, a National Mutual Acceptance Ethics Application will be submitted by the national lead. It is the responsibility of the local mini team at each site to ensure that the study is authorised appropriately by the site's Research and Governance Office (RGO), according to local regulations. HIPPO should be registered in the UK and ROI as a clinical audit.

Examples of audit registration forms can be found at the online project hub. When registering HIPPO as a clinical audit you can emphasis that:

- HIPPO is a national audit, and all data collected will measure current practice.
- No changes to normal patient pathways/ treatment will be made.
- All HIPPO data will be collected and stored online through a secure server running the Research Electronic Data Capture (REDCap) web application.¹⁴ REDCap allows collaborators to enter and store data in a secure system. Collaborators will be given secure REDCap project server login details, allowing secure data storage on the REDCap database.

Collaborators in the UK should seek their trust's Caldicott Guardian's permission to submit data to the REDCap system. No data should be uploaded to REDCap prior to written approval from the Caldicott Guardian. In Australia, no data should be uploaded to REDCap prior to written local governance authorisation. No patient identifiable information (e.g. NHS numbers) will be uploaded or stored on the REDCap database. All data should be handled in accordance with national and local data governance policies.

12. Quality assurance:

Design: This protocol was written with guidance from an expert cross-specialty advisory group. **Patient and Public Involvement**: The relevance of these research topics to patients were discussed with the NIHR Global Surgery Unit Community and Engagement Involvement (CEI) lead ([name]) and a Patient and Public Involvement lead of ACPGBI and ESCP ([name]). All these topics were felt to be important and relevant to patients. We will involve patient throughout the study and will produce patient facing materials after analysing the data.

Training: HIPPO National Leads are encouraged to hold local meetings with collaborating teams to brief them on the protocol, and to feedback any local issues or questions raised.

Project team structure: At each centre, this study can be delivered and disseminated by teams of medical students, junior doctors and/or consultants. Each team should include at least one specialist consultant to provide additional local support for participating medical students.

Data completeness: Following data collection, only data sets with >95% data completeness will be accepted for pooled national analysis. To emphasise the importance of data completeness to collaborators, data collection periods with >5% missing data points will be excluded from the study and collaborators from those periods withdrawn from the published list of citable collaborators.

Validation: This collaborative methodology for has been widely validated across multiple datasets, both nationally in the UK and Ireland and internationally, demonstrating high levels of case ascertainment (typically greater than 90 to 95%) and data accuracy (greater than 96 to 98%).^{16,17}

13. Authorship:

In accordance with National Research Collaborative (NRC) authorship guidelines¹⁸, all research outputs from HIPPO will be listed under a single corporate authorship ("NIHR Unit on Global Surgery").

All collaborators will be listed as PubMed-citable collaborators in accordance with the roles defined below (so long as the minimum requirements for authorship are met).

- Writing Group: A group of medical students, junior doctors, consultants and external advisory board members responsible for the overall scientific content, data analysis, and preparation of research manuscripts.
- Steering Committee: A core group of medical students, junior doctors and consultants
 who have overall responsibility for protocol design, project coordination, and data
 handling.
- Statistical Analysis: A small team of dedicated statisticians who take overall responsibility for the statistical analysis plan and quality assurance of data analysis

- National Leads: A network of surgeons and anaesthetists established with previous GlobalSurg and CovidSurg studies. They are responsible for national coordination of the study, acting as a link between mini-teams / hospital leads, and the steering committee.
 Requirements for authorship on HIPPO outputs include:
 - Active engagement with dissemination of HIPPO and other NIHR Unit on Global Surgery Collaborative activities at their country.
 - Effective and responsive communication with the steering committee, and with local collaborators throughout their time as Regional Leads.
 - Recruitment of centres.
 - Representation of NIHR Unit on Global Surgery Collaborative at regional educational and research meetings.
- Local (Hospital) Leads: A single lead point of contact for data collection at each site who has overall responsibility for site governance and coordinating handover between local collaborator teams. Local Leads should be prospectively identified by Regional Leads (although remain an optional role), and these are recommended to be the junior doctor or a senior medical student within the mini-team, and only one person can fulfil this role. A responsibility of the local (hospital lead) is to ensure that each mini-team is assigned a specialist consultant as supervisor.

Minimum requirements for authorship on HIPPO outputs include:

- Primary person responsible in obtaining local approvals for conduct of the HIPPO audit (e.g. obtaining local governance authorisation, adding the site to the HREC approval).
- Active involvement in a mini-team during a data collection period at the centre which meets the criteria for inclusion within the HIPPO dataset.
- Co-ordination of handover between all local collaborator teams at the centre, and involvement in local dissemination of HIPPO.
- Presentation of local results at their centre from the HIPPO audit (or otherwise arranges another collaborator to present on their behalf).
- Supervising Specialist Consultant: A supervising specialist consultant will be
 assigned for each mini team. The responsibilities of this role are to ensure that local
 guidelines are adhered to by all members of the mini-team and to ensure that any
 incidental findings made during the course of the data collection process are
 communicated to the treating inguinal hernia surgeon, according to local hospital
 policy.

- Local Collaborators (Data Collectors): A team of up to 5 people responsible for data
 collection per specialty group over a specific 4-week period at a particular centre. This
 should ideally be formed by a heterogeneous group with different levels of clinical
 training (e.g. medical students, trainees, consultants). Minimum requirements for
 authorship on HIPPO outputs include:
 - o Compliance with local audit approval processes and data governance policies.
 - Active involvement in data collection over at least one data collection period at a centre which meets the criteria for inclusion within the HIPPO dataset (below).
 - While assistance with other teams is encouraged, collaborator status will only be assessed based on successful completion of the allocated period.
 - Collaboration with the regional / local lead to ensure that the audit results are reported back to the audit office / clinical teams.

Criteria for centre inclusion within HIPPO:

- Obtain all appropriate local approvals for conduct of the HIPPO audit.
- Successful completion of at least one data collection period at the centre (with a minimum of one eligible patient per period included). Individual data collection periods will only be included when:
 - i. >95% data completeness has been achieved.
 - ii. All data for the period has been uploaded within the specified deadlines.

Please note if these criteria are not met, then the contributing mini-team and/or the centre may be removed from the dataset and authorship list (please get in contact as soon as potential issues arise so we can support as many centres to be included as possible).

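### The fixed 15 July 2023 date for destroying the Patient Identification Log falls 3 to 6 days before the last day 30 if the permitted one-month extension is used

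*Protocol*

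**What the plan says.** Four statements in the Protocol bear on this point.

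- **Surgery dates (section 3, Project Timeline).** "The suggested overall data collection periods will be Monday 30th January 2023 to 21st May 2023". The same bullet then leaves room for a longer run, "with the possibility of extending for 1 more month". The reason given is that ethical review may take different lengths of time in different countries. The last listed window is "Period 4: 00:00 24th April 2023 23:59 21st May 2023 (+ 30 Day Follow-up"). Section 3 and Appendix B list four periods, and no dates are given for an extension.
- **Who counts (section 3, last bullet).** "Patients should be included if their operation started (defined as 'knife-to-skin' time) within the time period". A patient operated on during the last day of a period is therefore eligible.
- **Follow-up (section 9).** Teams must "continue to review the medical record of each participant for a period of 30 days following the date of surgery". Sites set up their own system for this, and "The process will be facilitated by The Patient Identification Log".
- **The log (section 9).** It links the medical record number to the REDCap ID "to facilitate data entry and missing data requests". It is a hard copy that stays at the site, and the central unit cannot re-identify records. It is to be destroyed "immediately following the completion of the data collection phase of the study (15th July, 2023").

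**The concern.** Destruction of the log cannot be undone, and the Protocol puts a calendar date on it. The same document lets the last operation move by a month without moving that date. If the extension is used and the date is followed as printed, the link goes while some patients are still inside their 30 days and before their records can be queried.

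What is at stake is the secondary outcomes listed in section 8 (surgical site infection, reoperation, readmission and Clavien-Dindo complications, all at 30 days) and the ability to answer missing-data requests. Any loss would fall on sites that recruit in the extension. Given its stated purpose, those are likely to be sites in countries where ethical review is slower.

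**Working it through.** **Inputs.** Last listed surgery date: 21 May 2023 (section 3). Extension: one month (section 3), read as 28 days if it is one more standard period, as 30 days, or as a calendar month to 21 June. Follow-up: 30 days from surgery (section 9). Destruction date: 15 July 2023 (section 9).

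**Formulas.** Last day 30 = last surgery date + 30 days. Margin = 15 July − last day 30.

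| Reading | Last surgery | Last day 30 | Margin to 15 July |
|---|---|---|---|
| No extension | 21 May | 20 June | +25 days |
| 28-day extension | 18 June | 18 July | −3 days |
| 30-day extension | 20 June | 20 July | −5 days |
| Calendar month | 21 June | 21 July | −6 days |

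The Protocol's date equals the end of follow-up in none of these cases. Without the extension it is simply a later date with 25 days of slack, which is not an error. With the extension it is too early on every reading.

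**Patients affected.** The last operation with a full 30 days by the destruction date is 15 July − 30 days = 15 June.

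- 28-day extension: operations on 16, 17 and 18 June reach day 30 on 16, 17 and 18 July, so they lose 1 to 3 days.
- Calendar month: operations on 16 to 21 June reach day 30 on 16 to 21 July, so they lose 1 to 6 days.

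**Share of surgery days.** Of extension days: 3/28 = 10.7% or 6/31 = 19.4%. The listed periods cover 4 × 28 = 112 days, so of all surgery days: 3/(112 + 28) = 3/140 = 2.1% or 6/(112 + 31) = 6/143 = 4.2%. Read as shares of patients, these figures assume even operating across days; the second pair also assumes that recruitment in the extension matches the earlier periods.

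**Time for entry and queries.** The margin shrinks by one day for each later operation date. A patient operated on 22 May, the first extension day, reaches day 30 on 21 June and has 24 days. A patient operated on 15 June has none. The last extension patients have −3 to −6 days.

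**Would the missing-data exclusion follow?** Section 12 excludes periods with more than 5% missing data points. Suppose a centre recruits only in the extension and every follow-up field is blank for every affected patient. Follow-up fields would then have to make up more than 0.05 ÷ (3/28) = 46.7% of all fields, or more than 0.05 ÷ (6/31) = 25.8% for the calendar month. The field list is in the Data Summary Document, which is not at hand, so this cannot be settled. Appendix B step 11 words the limit differently, as more than 5% of a centre's patients having missing data. On the same assumptions, 10.7% or 19.4% would exceed that limit.

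**The case against.** The strongest reply is that nothing is wrong on the schedule as listed. The extension is a possibility, section 9 itself speaks of up to four periods, and for those the date leaves 25 days. This stands, and it makes the point conditional.

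The second reply is that the trigger is an event, completion of data collection, with the date only in brackets. If surgery is extended, data collection is not complete on 15 July, and a sensible site would wait. Appendix B step 6 supports this by tying secure storage of the hospital number to its use for 30-day follow-up. Section 9 also allows study documents in general to be destroyed at study completion or as local governance requires. This reading is available, but the sentence prints a date and does not say that it moves. A site that follows it literally acts within the Protocol and cannot reverse the step.

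Three stronger readings are tempting, and the document does not support them.

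- *Late patients could not be followed at all.* Section 9 presents the log as one means of linkage, and sites devise their own follow-up systems. Nothing establishes that no other route exists. Appendix B step 10 also asks for regular review throughout the 30 days, so most of each affected patient's follow-up should already be recorded.
- *Whole periods would be excluded for missing data.* As calculated, the data-point rule is reached only if follow-up fields form a large part of the dataset, which is unknown. The patient-level wording in Appendix B is easier to reach, but only if fields are actually left blank.
- *The primary outcome is compromised.* Compliance concerns waiting time and operative technique, which are known by the end of surgery. It would be touched only through exclusion of whole periods, which is not shown.

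**Conclusion.** The inconsistency is real but conditional. If the extension is used and 15 July is applied as printed, the log is destroyed 3 to 6 days before the last patient's day 30. Patients operated on after 15 June lose the last 1 to 6 of their 30 days under the Protocol's own linkage, and those operated on shortly before have little time for entry and queries. The effect is confined to secondary 30-day outcomes and query resolution at extension sites.

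The date result needs no assumption beyond the extension being used and the printed date being followed, and it holds for each reading of one month tried. It is worth correcting despite its small size, because destruction is irreversible and any loss would be concentrated in the sites that the extension is meant to serve.

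**What to change.** Replace the fixed date in section 9 with a rule: each site destroys its log once its last included patient has passed day 30 and the missing-data requests for that site are closed, subject to local governance. This agrees with Appendix B step 6.

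If a calendar date is preferred, keep 15 July for the listed periods and state a later one that applies when the extension is used. It must fall after 18 July for a 28-day extension or after 21 July for a calendar month, with time added for queries. The size of that margin is the sponsor's choice. As an illustration, keeping the present 25 days would give 12 August (18 July + 25 days) or 15 August (21 July + 25 days).

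The cost is one sentence. Extension sites would hold an identifying document a few weeks longer (28 to 31 days in the illustration), which may need a local governance notification.
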